## GALDERMA R&D

Protocol No.: RD.06.SPR.18131 V03 - 02 Dec 2015 eUS

Page 14 of 83

 Visit window of  $\pm$  3 days.

 Physical Examination to include: weight and review of systems: skin, cardiovascular, respiratory, abdomen, head and neck, musculoskeletal, neurological, lymph nodes and psychological. Height is to be evaluated at Screening visit only. Vital Signs to include: blood pressure, pulse rate

 Reconfirm that subject continues to meet inclusion/exclusion criteria.

 Total amount of Study Drug applied to involved skin should not to exceed 0.5 g/kg of body weight or 28g per day (whichever is the lower). First application to be made under the supervision of the investigator or designee. Record daily administration on dosing calendar. Dosing calendar to be checked at each visit after Baseline.

 Or at any time in case of early termination.

 The Cetaphil® Moisturizing Cream and Cetaphil® Gentle Skin Cleanser or equivalents will be provided by the Sponsor

 Events occurring after the Informed Consent Form and Assent Form (when applicable) have been signed should be recorded as Adverse Events in the eCRF

 Any therapy or medication other than study ointment will be noted on the Drugs/Therapies Form. Subjects that require a wash-out period of a prohibited therapy for >2 weeks, should be screen failed and may re-screen 1 time after completion of the washout period.

 PD Serum (non-fasting): calcium, phosphorus, albumin (in order to calculate the serum albumin-adjusted calcium) and PTH.

 PD Urine: Urine calcium and creatinine on 24-hour urine collection, whenever possible, or a urine sample after fasting for 4 hours in order to calculate Urine calcium : creatinine ratio. Subjects that are toilet-trained should be actively encouraged to complete 24-hour urine collection. A urine collection container/material will be given to the subject / subject's parent/legal guardian with the instruction to start collecting urine as of this visit and to bring the container back after the 24-hour/4-hour collection.

 Laboratory testing (full panel) will be completed at Week 30 for subjects in the PK group. For all other subjects, laboratory testing at Week 30 will be completed at Investigator's discretion.

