## 3 OVERALL CLINICAL TRIAL DESCRIPTION

This is an open-label, uncontrolled, multicenter long-term safety and efficacy study in pediatric subjects (age 2-16 years and 11 months, Version R03) with mild to moderate plaque psoriasis.

Approximately one hundred (100) subjects will be enrolled into this study. A subset of enrolled subjects (approximately 9 among the 100) will meet the PK requirements: pediatric subjects aged 2 to 6 years and 11 months (inclusive at Screening) and with a minimum 3% BSA involvement.

Qualified subjects will receive calcitriol 3 mcg/g ointment for a period of up to 26 weeks. The subject's parent/legal guardian or the subject under the responsibility of the parent/legal guardian will apply a thin film of study drug as needed to cover all involved areas twice daily, without exceeding a maximum of 0.5 g/kg of body weight or 28 g daily (whichever is the lower). If the subject experiences complete clearing of psoriasis per physician assessment (i.e. an IGA of 0), the subject should discontinue the study drug but continue to follow the visit schedule through the Week 26 visit. Treatment with study drug should be resumed if the IGA score is >0 and <4.

Subjects will be evaluated at screening, baseline and Weeks 4, 12, 26, and 30 as described in the Schedule of Assessments (Table 2). A visit window of  $\pm 5$  days will be allowed for Baseline and a visit window of  $\pm 3$  days will be allowed at the visits from Weeks 4 through 30.

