#### 8.1.4 Week 26 Visit / Early Termination visit

1. Document discussion with subject and parent/legal guardian in regards to continued willingness to participate in the study.
2. For post menarcheal females, collect a urine sample and perform a urine pregnancy test.
3. Record the % BSA involved by psoriasis (excluding face and scalp) (See Section 13.3).
4. Perform physical exam and record vital signs.
5. Obtain serum samples for routine blood chemistry, hematology, 1, 25(OH)2D, 25(OH)D and serum pharmacodynamic sampling and urine samples for urinalysis. Prepare them according to the Central Laboratory manual.
  - 5.1. For PD urine, get the 24-hour urine collection from subject or collect fasting (4 hour) urine sample when 24-hour collection is not possible.
  - 5.2. Provide a new container and instructions for 24-hour urine collection to be started 1 day prior to Week 30 Follow-up visit (for all subjects in the PK group and at the Investigator's discretion for all other subjects, such as in the case where the PD urine assessment from week 26 would be abnormal). The study site should contact the parent/legal guardian 48 hours prior to the visit to remind them to start the urine collection.
6. For selected subjects enrolled in the PK analysis: Collect blood sample for PK assessment.
7. Evaluate IGA.
8. Evaluate pruritus.
9. Question the subject's parent/legal guardian or subject (according to subject's maturity level) about the occurrence of Adverse Events. Non-persuasive open ended questions are to be asked, such as "Have you noticed any change in your health since last visit?"
10. Question the subject's parent / legal guardian or subject (according to subject's maturity level) specifically about symptoms of kidney stones e.g. obvious hematuria or pyuria, or vague abdominal or flank pain/ discomfort, or possible pain radiating to the groin area.
11. Ask the subject and parent/legal guardian whether there have been any changes to his/her concomitant therapies/procedures (added, removed, or changed) since the previous visit. Document all changes on the Drugs/Therapies form in the eCRF.
12. Check that the subject and/or parent/legal guardian has brought back all the study medication, even if unused, and check on compliance and review the dosing calendar.
13. Provide Cetaphil® Moisturizing Cream and Cetaphil® Gentle Skin Cleanser or equivalents to the subject's parent/legal guardian.

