### 8.1.5 Week 30 Follow-up visit

1. For post menarcheal females, collect a urine sample and perform a urine pregnancy test.
2. Record the % BSA involved by psoriasis (excluding face and scalp) (See section 13.3, Appendix 3).
3. Obtain serum samples for laboratory testing (full panel) for subjects in the PK group. For all other subjects, obtain serum samples for laboratory testing at the Investigator's discretion (all subjects). Obtain urine for urinalysis (all subjects).
4. Obtain serum samples for 1,25(OH)2D, 25(OH)D and serum PD parameters for subjects in the PK group. For all other subjects, obtain serum samples at the Investigator's discretion. Prepare them according to the Central Laboratory manual.
5. Obtain 24-hour urine sample for PD urine for subjects in the PK group and send it to the central lab for analysis. For all other subjects, obtain 24-hour urine sample at the Investigator's discretion and send it to the central lab for analysis.
6. For selected subjects enrolled in the PK analysis: Collect blood sample for PK assessment.
7. Evaluate IGA.
8. Evaluate pruritus.
9. Question the subject's parent/legal guardian or subject (according to subject's maturity level) about the occurrence of Adverse Events. Non-persuasive open ended questions are to be asked, such as "Have you noticed any change in your health since last visit?"
10. Question the subject's parent / legal guardian or subject (according to subject's maturity level) specifically about symptoms of kidney stones e.g. obvious hematuria or pyuria, or vague abdominal or flank pain/ discomfort, or possible pain radiating to the groin area.
11. Ask the subject and parent/legal guardian whether there have been any changes to his/her concomitant therapies/procedures (added, removed, or changed) since the previous visit. Document all changes on the Drugs/Therapies form in the eCRF.
12. After collecting all data from the subject (including laboratory samples results), complete the Exit form of the eCRF.

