### **10.5.2 Amendments**

The Sponsor may modify the clinical trial protocol at any time for ethical, medical, or scientific reasons.

No amendment can be implemented at clinical trial centers, unless to eliminate an immediate hazard to the subjects, without having been submitted to FDA for its review and having obtained approval from the IRB with responsibility for review and approval of the clinical trial.

Once this amended protocol is implemented by each study center, it will apply to newly enrolled subjects at that site. Current subjects will continue to follow the original protocol through to completion.

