- ⁸ Any therapy or medication other than study ointment will be noted on the Drugs/Therapies Form. Subjects that require a wash-out period of a prohibited therapy for >2 weeks, should be screen failed and may re-screen 1 time after completion of the washout period.
- ⁹ PD Serum (non-fasting): calcium, phosphorus, albumin (in order to calculate the serum albumin-adjusted calcium) and PTH.
PD Urine: Urine calcium and creatinine on 24-hour urine specimen, when feasible or fasting (4 hours) urine sample in order to calculate Urine calcium: creatinine ratio. Subjects that are toilet-trained should be actively encouraged to complete 24-hour urine collection. A urine collection container/material will be given to the subject / subject's parent/legal guardian with the instruction to start collecting urine as of this visit and to bring the container back after the 24-hour/4-hour collection.
- ¹⁰ Unscheduled visit: When necessary and exceptionally, because of either an AE needing a specific treatment, AE leading to withdrawal from the study, or other reason. An ongoing dialogue between subject, parent/legal guardian and investigators focusing on all aspects of the trial is encouraged. Any new information that arises in relation to the trial and that might affect the willingness of the subject and/or parent/legal guardian should be discussed. This brief discussion should be documented during each study visit.
- ¹¹ Subjects rolling over from SPR.18132 may omit the Screening Visit and proceed directly to the Baseline Visit after receipt of all required SPR.18132 Week 8 lab results and confirmation that the subject meets all inclusion and no exclusion criteria. Naïve subjects must complete the SPR.18131 Screening visit per Table.
- ¹² Lab assessment should only be done at Week 30 visit if results were abnormal at the Week 26/ET visit.
- ¹³ Any subjects with suspected kidney stones are to be referred to the subject's PCP for treatment and the IDMC will be consulted on a case-by-case basis.
- ¹⁴ The visit before: Distribute container and provide instructions for 24-hour urine collection to be started 1 day prior to Week 12 and Week 26/ET visits. The study site should contact the parent/legal guardian 48 hours prior to the visit to remind them to start the urine collection.
- ¹⁵ Subjects may re-screen one time with written approval from the Sponsor prior to re-entry into the study.
- ¹⁶ At Baseline, the study nurse show the subject's parents how to apply the drug.

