7.3.3 Laboratory Parameters

Analysis visit will be applied for the laboratory parameter summaries.

Descriptive statistics for each laboratory parameter will be provided for scheduled visit and for the changes from Screening at each post-baseline visit. “Final” visit (Week 26 (Final)) will be defined as the last post-baseline available observation during the treatment period.

A shift table for the laboratory data at Screening versus Final will be constructed for laboratory parameters for which numeric reference ranges are available. The number of subjects below, within, and above the laboratory reference ranges at Screening versus Final will be summarized.

For each laboratory test, a complete data listing will be provided for subjects who have any laboratory results outside the reference ranges, and for subjects who have any laboratory results with clinical significance.

Plot of mean change from screening and spaghetti plot (all-subjects-in-one figure or selective individual subject figure) will be used to explore the trend of laboratory data change over the study, especially for serum albumin-adjusted calcium, urine calcium/creatinine ratio, phosphorus, PTH. Box-and-Whisker plots for PTH and Calcium/Creatinine ratio by visit will be constructed for data exploration.

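### Week 30 calcium-metabolism and vitamin D results come from a subset at least partly chosen by its Week 26 results, yet the SAP summarises them as an ordinary visit, so the Week 30 row is not comparable with Week 26

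*SAP*

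**What the plan says.** **Who is tested, SAP.** Table 1 attaches footnote 12 to three Week 30 rows: serum PD, urine PD, and 25(OH)D with 1,25(OH)2D. The footnote reads "Lab assessment should only be done at Week 30 visit if results were abnormal at the Week 26/ET visit". The two PD rows supply all four key laboratory variables of SAP 4.2: albumin-adjusted calcium, urine calcium:creatinine ratio, phosphorus and PTH. The footnote is not attached to routine chemistry and hematology, or to urinalysis.

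**Who is tested, protocol V03.** Table 2, footnote 11, has a different rule: "Laboratory testing (full panel) will be completed at Week 30 for subjects in the PK group", and then "For all other subjects, laboratory testing at Week 30 will be completed at Investigator's discretion". Section 3 puts the PK group at "approximately 9 among the 100". Section 8.1.4 gives one example of that discretion, for the repeat 24-hour urine: "such as in the case where the PD urine assessment from week 26 would be abnormal". Section 8.1.5 takes urinalysis in everyone.

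**Which rule applies.** Section 10.5.2 applies the amendment to newly enrolled subjects and adds: "Current subjects will continue to follow the original protocol through to completion". More than one Week 30 rule may therefore feed one dataset.

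**How the results are summarised.** SAP 7.3.3: "Descriptive statistics for each laboratory parameter will be provided for scheduled visit and for the changes from Screening at each post-baseline visit". It adds mean-change plots, spaghetti plots, and box plots by visit for PTH and the calcium:creatinine ratio. SAP 7.5 summarises laboratory data by analysis visit and makes no exception for Week 30. The shift table stops at the last on-treatment value.

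**The concern.** Safety is the primary objective, and calcium metabolism is the main systemic question. The shift table ends on treatment, so the by-visit summaries, plots and listings are the only planned outputs that show these laboratory values after the drug is stopped. A reader will use Week 30 to judge whether a change in calcium or PTH reverses off treatment.

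If a child is tested at Week 30 because of the Week 26 result, the Week 30 row is not the trial population. Its number and case-mix differ from Week 26, and any difference between the two rows mixes drug withdrawal with selection.

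**Working it through.** The plan states no figure on this point and gives neither the rate of abnormal results nor the visit-to-visit correlation. Both are assumed below and varied. Values are in SD units with mean 0 where there is no drug effect.

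**1. Share of the Week 30 group that is selected.** Under footnote 12 it is 100%. Under V03, suppose discretion adds only abnormal non-PK children, a fraction p of the 100 − 9 = 91. The selected share is then 91p / (91p + 9):
- p = 2.5%: 2.275/11.275 = 20%
- p = 5%: 4.55/13.55 = 34%
- p = 24% (adult hypercalcemia rate in protocol 1.3, used only as an upper end): 21.84/30.84 = 71%

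Selected children are the majority only if p exceeds 9/91 = 9.9%.

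**2. By-visit mean, one-sided selection, no drug effect.** For a cut-off c exceeded by a fraction p, and correlation ρ, the mean at Week 30 given Week 26 > c is ρφ(c)/p. With c = 1.96, φ(c)/p = 0.0584/0.025 = 2.34.

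| ρ | Week 26, all | Week 30, selected only | Above limit at Week 30 (2.5% at Week 26) | Week 30 with 9 unselected PK children |
|---|---|---|---|---|
| 0.5 | 0 | +1.17 | 18.5% | 2.275 × 1.17/11.275 = +0.24 |
| 0.7 | 0 | +1.64 | 33% | +0.33 |
| 0.8 | 0 | +1.87 | 44% | +0.38 |

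Over p = 2.5% to 24% and ρ = 0.3 to 0.9, the Week 30 mean is +0.39 to +2.10 SD with selected children only, and +0.14 to +0.85 SD with the PK group added.

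**3. With a drug effect.** This was simulated with 1,000,000 children, a true shift of 0.5 SD, ρ = 0.5, and Screening values above the limit excluded (as the protocol does for calcium, calcium:creatinine and PTH).
- *No recovery after stopping:* the mean goes from 0.47 (Week 26, all) to 1.38 (Week 30, selected). The share above the limit goes from 6.4% to 25.1%.
- *Full recovery:* the mean goes from 0.47 to 0.87, although the true all-children mean at Week 30 is −0.03.

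The first looks like worsening, and the second hides recovery.

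**4. Change from Screening, no drug effect.** With equal correlations, selection raises the Screening value by the same ρφ(c)/p, so the expected change is 0. Excluding Screening values above the limit makes it +0.19 (ρ = 0.5) or +0.22 (ρ = 0.7). In step 3 it goes from 0.53 to 0.64 without recovery and from 0.53 to 0.13 with it, so this display follows the truth much better.

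**5. Two-sided selection, no drug effect.** By symmetry the mean is 0, but the SD is √(1 + ρ² × 1.96 × 2.34) = 1.46, 1.80 and 1.98 for ρ = 0.5, 0.7 and 0.8, against 1 in all children. Excluding high Screening values leaves a small negative mean (−0.16 at ρ = 0.5, −0.39 at ρ = 0.7). Box plots would show the extra spread.

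**6. Same children, Week 26 to Week 30, one-sided, no drug effect.** The expected change is (ρ − 1) × 2.34 = −1.17, −0.70 and −0.47 SD. By chance alone 81.5%, 67% and 56% are back in range.

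**The case against.** The strongest reply is that the study is descriptive, Week 30 is already labelled as follow-up, the shift table does not use it, and change from Screening is close to unbiased. All of that is correct. It narrows the problem to the by-visit values, the box plots and the individual traces, but the SAP gives the reader no sign that the Week 30 row is selected.

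The size is also uncertain. Footnote 12 says only that a result was abnormal. Low PTH is a stated concern (protocol 5.6), so selection may be two-sided and the mean bias small. The SAP does not say whether one abnormal result triggers the whole panel. If it does, selection on any one parameter is diluted: with six independent parameters at 5% each, 1 − 0.95⁶ = 26% of normal children would qualify.

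Three stronger readings are tempting but not supported:
- **That the by-visit table gives a false picture of recovery.** It compares all children at Week 26 with selected children at Week 30, so one-sided selection pushes the mean towards worsening. False recovery arises only when the same children are followed, as in the spaghetti plots of SAP 7.3.3 and the listings and individual plots of SAP 9.3. The SAP plans no paired table.
- **That all Week 30 laboratory data are affected.** Footnote 12 leaves out urinalysis and routine chemistry and hematology. (Protocol footnote 11 does make routine chemistry and hematology discretionary outside the PK group.)
- **That Week 30 is mainly selected children whichever rule applies.** That is certain only under footnote 12. Under V03 it depends on the abnormality rate and on how discretion is used, and the one example given concerns urine only.

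**Conclusion.** The point holds for Week 30 serum PD, urine PD and vitamin D results. Followed as written, the SAP yields a Week 30 row that is wholly result-selected under footnote 12, or partly so under V03 where discretion follows Week 26 results, and it presents that row as comparable with Week 26.

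With one-sided selection above 1.96 SD, no drug effect and ρ of 0.5 to 0.8, the by-visit mean goes from about 0 to +1.2 to +1.9 SD if only selected children are tested, and to +0.24 to +0.38 SD if the 9 PK children are added. With two-sided selection the mean bias largely cancels but the spread is inflated. Within-child traces carry the opposite error. So the planned displays can mislead in either direction, and neither can be read as evidence for or against reversal. The SD figures rest on assumed normality, abnormality rate and correlation. That the rows are not comparable whenever testing depends on the Week 26 result does not rest on those values.

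**What to change.** In SAP Table 1, 7.3.3 and 7.5:

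1. Align the Week 30 laboratory rule with protocol V03, and state which rule governed subjects enrolled before the amendment.
2. Take Week 30 PD and vitamin D values out of the by-visit means, mean-change plots and box plots.
3. Report them in a separate follow-up table with the number tested and the reason for testing. Show the PK group, who are all tested, apart from children tested under footnote 12 or at discretion, and label the latter as selected.
4. If paired Week 26 and Week 30 values or individual traces are shown, state that a return towards normal in the selected children is expected from regression to the mean and is not evidence of reversal.

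The cost is SAP text and table layout. No visit, sample or protocol procedure changes.

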3.1 Efficacy Assessment

3.1.1 Efficacy Measurements

IGA and Pruritus evaluations will be assessed at each visit on all treated areas.

3.1.1.1 IGA (as evaluated on all treated areas by a Board Certified Dermatologist)

The IGA will be evaluated at each visit on a 0 to 4 point scale. The following definitions will be used to score IGA:

0	Clear	No signs of psoriasis except for residual hypopigmentation / hyperpigmentation
1	Almost Clear	Just perceptible erythema, no induration, and no scaling
2	Mild	Mild erythema, no induration, and mild or no scaling
3	Moderate	Moderate erythema, mild induration, and mild or no scaling
4	Severe	Severe erythema, moderate to severe induration, and scaling of any degree

3.1.1.2 Pruritus (as evaluated on all treated areas)

Pruritus will be evaluated at each visit and scored on a 0 to 4 point scale. The following definitions will be used to score Pruritus:

Pruritus: an itching sensation.

0	None	No-itching
1	Mild	Slight itching, not really bothersome
2	Moderate	Definite itching that is somewhat bothersome without loss of sleep
3	Severe	Intense itching that has caused pronounced discomfort, night rest interrupted
4	Very Severe	Very severe itching that has caused pronounced discomfort during the night and daily activities

3.1.1.3 Other Assessments:

Percent Body Surface Area (BSA) involved will be assessed using the methodology shown in Protocol, Section 13.3, Appendix 3 (Calculation of Percent Body Surface Area Involved).

3.2 Safety Assessment

A safety assessment will be conducted for all subjects at the screening visit (from the Informed consent signature) and every subsequent visit. The safety parameters are AEs, laboratory safety tests, physical examination, and vital signs.

3.2.1 Adverse Events (AE)

Adverse events (AEs) are to be monitored throughout the course of the clinical trial (from the subject signed the Informed Consent Form to the end of the subject's participation). All AEs are to be reported on the Adverse Event Form of the eCRF with complete information as required, including onset/end dates of AEs, severity of AEs, relationship to the study drug, serious AEs and AEs of special interest.

3.2.2 Laboratory Safety Tests

The following laboratory safety tests will be performed according to the Schedule of Assessments.

- Hematology:

White blood cell (WBC) count with differential, red blood cell (RBC) count, hemoglobin (Hb), hematocrit (hct), mean cell volume (MCV), and platelet count (Plt)

- Blood chemistry (non-fasting):

Total protein, alanine aminotransferase (ALT) (SGPT), aspartate aminotransferase (AST) (SGOT), alkaline phosphatase (ALP), blood urea nitrogen, creatinine, and bilirubin (total and conjugated).

- Urinalysis:

A semi-quantitative urinalysis will be performed. The following parameters will be evaluated: glucose, ketones, blood, proteins, leukocytes, and nitrites.

- Pharmacodynamic parameters:

Serum (non-fasting): calcium, phosphorus, albumin (in order to calculate the serum albumin-adjusted calcium), PTH

Urine: Calcium and creatinine (in order to calculate urine calcium:creatinine ratio) on 24-hour urine specimens, when feasible, or fasting (4 hours) urine samples

- Other Assessments

- 1, 25(OH)2D
- 25(OH)D

- Urine Pregnancy Test

Post menarcheal female subjects of childbearing potential will have a urine pregnancy test performed at all visits. For pre-menstrual subjects who begin menses after the Screening visit, pregnancy tests will be performed according to the Schedule of Assessments for females of childbearing potential (Baseline, Week 4, Week 8, Week 12, Week 20, Week 26/ET, and Week 30).

